### 11.1.2 Minor Protocol Deviations

The categories for the minor deviations will include, but are not limited to the deviations presented in **Table 22**.

**Table 22: Definition of Minor Protocol Deviation Categories**

Category	Description
Concomitant medication	Use of drugs which are known to affect CYP2A6 or CYP1A2 activity.
Procedural violation	Violation of planned procedure Assessments not taken at the correct time or within the allowed time window (see Table 23 )
Time deviation (Questionnaires)	Assessments not taken at the correct time or within the allowed time window (see Table 23 )
Time deviation (Blood draws)	Assessments not taken at the correct time or within the allowed time window (see Table 23 )
Time deviation (CYP1A2 activity)	Assessments not taken at the correct time or within the allowed time window (see Table 23 )
Time deviation (CYP2A6)	Assessments not taken at the correct time or within the allowed time window (see Table 23 )
Time deviation (Assessment of cough)	Assessments not taken at the correct time or within the allowed time window (see Table 23 )
Time deviation (CO breath test)	Assessments not taken at the correct time or within the allowed time window (see Table 23 )
Time deviation (Oxysterol, nasal epithelial, transcriptomics and buccal collections)	Assessments not taken at the correct time or under the correct food restrictions (see Table 23 )
Time deviation (4-hour urine fraction collection)	Assessments not taken at the correct time or within the allowed time window (see Table 23 )
Time deviation (HST Recording)	Assessments not taken at the correct time or within the allowed time window (see Table 23 )
Visit window deviation	Day 30, Day 60 and Day 90 Visits outside of visit window (see Table 23 ).
Time missing	Assessment date or time is missing
Assessment missing	Assessment is missing
Visit missing	Scheduled visit not done

### 11.1.3 Assessment Windows

During the confinement period, smoking of the randomized products should take place within the 06:30 AM and 11:00 PM window.

The assessment windows are shown in **Table 23**.

**Table 23: Assessment Windows**

Assessment	Nominal Time point(s)	Window
24 h urine sample	Start (Days -1 to 5)	06:30 AM $\pm$ 30 min
	Start (Days 30, 60 and 90)	09:00 AM $\pm$ 30 min
	End (Days 0 to 6)	06:29 AM $\pm$ 30 min
	End (Days 31, 61 and 91)	08:59 AM $\pm$ 30 min
4 h urine sample	Start (Day -1)	10:30 AM $\pm$ 20 min
	Start (Day 91)	Immediately after end of 24-hour urine collection
	End (Day -1)	02:00 PM $\pm$ 30 min
	End (Day 91)	Before 02:30 PM
CYP1A2 activity in plasma	Day 0, Day 5 and Day 90	6 h after intake of caffeine tablet $\pm$ 15 min
CYP2A6 activity	Day 0, Day 6 and Day 91	Prior to smoking / product use
CO breath test	Day -2	Time of admission to 06:30 PM
	Morning (Days -1 to 5)	Irrespective of product use
	Day -1 to Day 5	To be done within 15 minutes prior to product use (for THS 2.2 Menthol and mCC arms) or between 08:00 AM and 09:30 AM (SA arm).
	Day 6	Between 12: 00PM 01:30 PM, 04:00 PM and 05:30 PM, and 08:00 PM and 09:30 PM
	Day 30 and Day 60	Prior to discharge. Irrespective of product use.
	Day 90	Between 10:00 AM and 11:30 AM. Irrespective of product use.
		Between 10:00 AM and 12:30 AM. Irrespective of product use.
Assessment of Cough	Days 0 to 6	To be done prior to product use but not later than 10:00 AM.
	Day 31 and Day 61	Irrespective of product use but no later than 10:00 AM
	Day 91	Prior to smoking but no later than 10:00 AM
MNWS questionnaire	Day 0 to 6	To be done prior to product use but not later than 10:00 AM

Assessment	Nominal Time point(s)	Window
	Day 31 and Day 61	Irrespective of product use but no later than 10:00 AM
	Day 91	To be done prior to product use but no later than 10:00 AM
QSU-brief questionnaire	Days -1 to 5, Days 30, 60 and 90	08:00 PM to 11:00 PM
mCEQ questionnaire	Days -1 to 5, Days 30, 60 and 90	08:00 PM to 11:00 PM
Behavioral Risk Factor Questionnaire, SQ and Supplemental questions Nicotine and cotinine in plasma	Days -1 and 5	08:00 PM to 11:00 PM
	Days 0 to 4	08:00 PM to 09:30 PM
	Day 5 for THS 2.2 Menthol and mCC arms: within 15 minutes before first product use ( $T_0$ ): then additional blood samples at 2 hour intervals from $T_0$ until 11:00 PM. In SA arm only one blood sample between 08:00 PM to 09:30 PM	Each sample has a 5 minute time window
	Day 6 for THS 2.2 Menthol and mCC arms: 20 and 24 h after $T_0$ of Day 5. In SA arm only one blood sample between 08:00 AM to 09:30 AM	5 minute time window
	Day 30 and Day 60	10:00 AM-11:30 AM irrespective of product use
	Day 90	10:00 AM-12:30 PM irrespective of product use
COHb blood sampling	Days -1 to 4	08:00 PM to 09:30 PM
	Morning sample on Day 5	Within 15 minutes prior to product use (for THS 2.2 Menthol and mCC arms) or between 08:00 AM and 09:30 AM (SA arm)
	Day 5 other samples	Between 12:00 PM and 01:30 PM, 04:00 PM and 05:30 PM, and 08:00 PM and 09:30 PM
	Day 30 and Day 60	Irrespective of product use between 10:00 AM and 11:30 AM.
	Day 90	Irrespective of product use

Assessment	Nominal Time point(s)	Window
Oxysterols and Blood sampling for bio-banking for transcriptomics	day 0, day 6 and Day 91	between 10:00 AM and 12:30 AM. Has to be done after at least 10 hours of fasting.
Nasal Epithelial Collection and Buccal Collection	Day 0 and Day 90	In the afternoon before 9:00 PM. Subject must not have eaten at least 30 minutes prior to collection
	Day 6	Prior to discharge. Subject must not have eaten at least 30 minutes prior to collection
HST Questionnaire	Day 0 Day 4, Day 30, Day 60 and Day 90 for all subjects in the THS 2.2 Menthol and mCC arms	08:00 PM-11:00 PM 08:00 PM-09:30 PM
HST Recording	Day 0 Day 1 and Day 4 for all subjects in the THS 2.2 Menthol and mCC arms smoking compatible mCC Day 30, Day 60 and Day 90 for all subjects in the THS 2.2 Menthol and mCC arms smoking compatible mCC	06:30 AM-11:00 PM 06:30 AM-11:00 PM Start time: 08:30 AM to 09:30 AM. End time: 12:30 PM to 01:30 PM. 4-hour recordings ± 15 min
Ambulatory Visit	Day 30, Day 60 and Day 90 Visits	± 5 days.

## 12 PLANNED STATISTICAL METHODS

### 12.1 General Considerations

Data analysis will be performed using SAS® Version 9.3.

Data listings will be provided for all data collected as defined in the protocol, ordered by randomization arm and subject, Day, Visit and time point (if applicable), unless otherwise stated. Summary statistics and statistical analysis will only be presented for data where detailed in this SAP. All unscheduled assessments will be included in the listings.

#### 12.1.1 Stratified Presentation

The following summaries will be produced by randomization arm, stratified by sex (male vs. female) and mCC consumption (10-19 mCC/day vs. >19 mCC/day) for the PP set at period 1 and 4:

- Demographics and Baseline Characteristics
- COHb, and MHBMA, 3-HPMA, S-PMA and total NNAL adjusted for creatinine.
- Product use

Summaries of data by product use categories will be produced for the product use time periods 1 to 4 (see **Table 25**), as appropriate.

Summaries of safety data will be provided stratified by pre-randomization and randomized period (see **Table 25**).

All endpoints will be summarized stratified by time point as appropriate.

#### 12.1.2 Subgroup Analyses

No subgroup analyses will be performed in this study.

#### 12.1.3 Descriptive Statistics

For continuous data, summary statistics will include the number of subjects (n), the number and percent of subjects with missing data, the arithmetic mean, arithmetic standard deviation (SD), 95% confidence interval (CI), median, first and third quartiles, minimum and maximum; for log-normal data the geometric mean, geometric 95% CI and geometric coefficient of variation (CV) will also be presented. For categorical data, frequency counts and percentages will be presented. Data listings will include all subject level data collected unless otherwise specified.

Unless otherwise specified, data described over time will be reported for periods 2-4 (see **Table 25**).

Data for early termination will be summarized at the end of the corresponding period (1-4). Data for early termination collected during an unplanned ambulatory visit will be handled as specified in Section 12.1.6 “Handling of Unplanned Data”.

#### Urinary BoExp Summaries

In general, urinary BoExp will be described over time as follows:

- Summary of concentration values adjusted for creatinine, and their percent change from baseline. Line graphs will be produced for arithmetic means of creatinine adjusted concentration (and 95% CI of the mean) for the percent change from baseline over all timepoints.
- Summary of quantity excreted over 24-hours values.

In general, BoExp measured in blood or breath tests will be described with summaries of the levels over time and levels expressed as percent change from baseline. BoExp levels will also be presented with line graphs.

Summaries and graphs will be produced for the FAS and PP Set. All derived variables will be listed together with the raw BoExp levels.

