## 7 DERIVED AND COMPUTED VARIABLES

Mean change from baseline (baseline is defined in Section 12.1.4 “Definitions for Statistical Data Analysis”) is the mean of all individual subjects’ change from baseline values. Each individual change from baseline will be calculated by subtracting the individual subject’s baseline value from the value at the timepoint. The individual subject’s change from baseline values will be used to calculate the mean change from baseline.

Mean percent change from baseline is the mean of all individual subjects’ percent change from baseline values. Each percent change from baseline will be calculated by subtracting the individual subject’s baseline value from the value at the desired timepoint and then dividing this calculated value by the individual subject’s baseline value and multiplying by 100. These individual subjects’ percent changes from baseline values will be used to calculate the mean percent change from baseline.

When the baseline value is 0, 1 will be used in the denominator for calculating the percent change from baseline.

The QT interval corrected using Bazett’s formula (QTcB) will be calculated as follows:

$$QTcB = \frac{QT}{\sqrt[2]{\frac{60}{HR}}}$$

The QT interval corrected using Fridericia’s formula (QTcF) will be calculated as follows:

$$QTcF = \frac{QT}{\sqrt[3]{\frac{60}{HR}}}$$

Reported BMI will be calculated at site from the body weight and height using the following formula:

$$BMI = \frac{\text{weight in kilograms}}{\text{height in meters}^2} \quad (\text{kg/m}^2)$$

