### 12.6.1 Primary Analyses

#### 12.6.1.1 Analysis of Biomarkers of Exposure for Primary Endpoints

The BoExp (COHb in blood and urinary concentrations of MHBMA, 3-HPMA, S-PMA and Total NNAL) used for the primary analysis will be summarized as detailed in Section 12.1.3 “Descriptive Statistics”. The listing of the COHb data will have a flag for whether a subject’s COHb was <2%.

The baseline is as defined in Section 12.1.4 “Definitions for Statistical Data Analysis”.

The primary endpoints will be log-transformed (basee) prior to analysis. The analysis will compare the evening COHb level (20:00-21:30 PM) on Day 5; and urinary concentrations of MHBMA, 3-HPMA and S-PMA adjusted for creatinine on Day 5 and urinary concentrations of Total NNAL adjusted for creatinine on Day 90 Visit between the THS 2.2 Menthol and mCC arms for the PP Set. An analysis of covariance (ANCOVA) (Snedecor and Cochran 1982) model will be used with terms for the log-transformed baseline value, sex, average daily mCC consumption over the last 4 weeks as reported during screening and randomization arm.

The SAS code to be used for the THS 2.2 Menthol and mCC data is shown below:

```
Proc glm data=_data_;
Class randomization_arm sex cigarette_cons;
Model log_biomarker = log_baseline sex cigarette_cons
randomization_arm;
Lsmean randomization_arm / pdiff =control('mCC') alpha=0.05 cl;
Run;
```

The least squares (LS) means and estimate of the difference and the 95% CI will be back-transformed. The geometric LS means for each randomization arm along with the ratio

(THS 2.2 Menthol : mCC), two-sided 95% CI and one-sided p-value will be presented in the tables. THS 2.2 menthol : mCC effects will be graphed in a forest plot.

All figures, summaries and analyses will be performed on the PP Set. Additional descriptive statistics will be provided within the secondary analysis.

The data will be presented in the below outputs:

TFL number	Title
FIGURES	
15.1.1.1	Forest Plot of Statistical Analysis of Biomarkers of Exposure on Day 5 and Day 90 – PP Set
15.1.1.2	Biomarkers of Exposure Geometric Mean and 95% CI – PP Set
TABLES	
15.2.3.1.1	Analysis of COHb, MHBMA, 3-HPMA, S-PMA and Total NNAL on Day 5/90 Visit for THS 2.2 Menthol versus mCC for the Primary Objective – PP Set
15.2.4.1.1	Descriptive Statistics of Blood COHb (%) – PP Set
15.2.4.1.1.1	Descriptive Statistics of Blood COHb (%) by Sex – PP Set

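### Averaging individual percent changes from baseline shows a spurious average rise in log-normal biomarkers; this affects descriptive outputs only

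*SAP*

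**What the plan says.** SAP 7 fixes the measure: "Mean percent change from baseline is the mean of all individual subjects"' own percent changes, each being the change divided by that subject's baseline, times 100.

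SAP 12.1.3 then applies it. Under Urinary BoExp Summaries it asks for: "Summary of concentration values adjusted for creatinine, and their percent change from baseline". It also asks for a graph: "Line graphs will be produced for arithmetic means of creatinine adjusted concentration (and 95% CI of the mean) for the percent change from baseline". For biomarkers in blood and breath (COHb and exhaled CO) the same section tabulates percent change but plots levels only. Both are to be produced for the FAS and the PP Set. The general list of statistics for continuous data in 12.1.3 includes the arithmetic mean with its 95% CI and the median, and "for log-normal data the geometric mean, geometric 95% CI and geometric coefficient of variation (CV) will also be presented".

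The inferential sections work on another scale. SAP 12.6.1.1 says "The primary endpoints will be log-transformed", and afterwards: "The least squares (LS) means and estimate of the difference and the 95% CI will be back-transformed". SAP 12.6.2.1 puts every biomarker of exposure except the CO breath test on the log scale.

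The figures listed for the primary, sensitivity and secondary analyses (15.1.1.2 in 12.6.1.1, 15.1.1.3 in 12.6.1.3, 15.1.1.4 in 12.6.2.1) are all titled "Biomarkers of Exposure Geometric Mean and 95% CI", followed by the analysis set.

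**The concern.** The plan models these biomarkers as log-normal when it tests them but measures change on a scale that does not suit log-normal data. A subject whose baseline happens to be low by chance contributes a large positive percent change. A subject whose baseline is high by chance contributes a negative one that cannot go below −100%. The two do not cancel, so the average is above zero even if nothing has changed. The measure is also not reversible: taking Day 5 as baseline for Day 0 would show a rise in that direction too.

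The mCC arm, where no change is expected, is where this is most visible. Continuing smokers could appear to increase their exposure in a table or graph although their typical level is unchanged.

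The geometric mean that SAP 12.1.3 adds for log-normal data does not repair this column. It serves for levels, but a geometric mean cannot be taken of percent changes, many of which are negative.

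**Working it through.** **Inputs.** CVs from SAP Table 16 (COHb 0.32, 3-HPMA 0.50, MHBMA 0.70, S-PMA 0.70), Table 17 (Total NNAL 0.60) and Table 18 (COHb 0.14, 3-HPMA 0.20, MHBMA 0.47, S-PMA 0.50). Sample sizes from Table 19 (80:40, and 40:40 for Total NNAL). The correlation rho between a subject's log baseline and log follow-up value is not in the documents. It is an assumption here, shown from 0 to 0.9.

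**Check that the CVs are log-normal between-subject spread.** The documents give no figure for the bias, but Table 20 gives a power that uses the same CVs. Take s² = ln(1 + CV²) and, for each marker, power = Φ(ln(0.5/MR)/SE − 1.96), with SE = s·√(1/n₁ + 1/n₂).

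- COHb: s = 0.312, SE = 0.312 × √(1/80 + 1/40) = 0.0605, ln(0.5/0.40) = 0.223, power 0.958.
- Total NNAL: s = 0.555, SE = 0.555 × √(1/40 + 1/40) = 0.124, ln(0.5/0.30) = 0.511, power 0.985.
- 3-HPMA, MHBMA and S-PMA: practically 1.

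The product is 94.3% (93.9% with the t distribution), against 94% in Table 20. The Table 18 set gives 98.2% against 98%. This reading of the CVs is therefore sound.

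**Bias formula.** Let baseline X and follow-up Y be log-normal with equal log means, log variance s² and log-scale correlation rho. Then ln(Y/X) has mean 0 and variance 2s²(1 − rho), so E(Y/X) = exp(s²(1 − rho)). The expected mean percent change is 100·(exp(s²(1 − rho)) − 1), although the median ratio is exactly 1.

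**Apparent rise with no true change, CVs of Tables 16 and 17:**

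| Marker | CV | s² | rho 0.5 | rho 0.8 |
|---|---|---|---|---|
| COHb (tabulated only) | 0.32 | 0.0975 | +5.0% | +2.0% |
| 3-HPMA | 0.50 | 0.2231 | +11.8% | +4.6% |
| Total NNAL | 0.60 | 0.3075 | +16.6% | +6.3% |
| MHBMA, S-PMA | 0.70 | 0.3988 | +22.1% | +8.3% |

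With the Table 18 CVs at rho 0.5 the figures are +1.0% (COHb), +2.0% (3-HPMA), +10.5% (MHBMA) and +11.8% (S-PMA).

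At CV 0.70 across rho: +49.0% (rho 0), +32.2% (0.3), +22.1% (0.5), +12.7% (0.7), +8.3% (0.8), +4.1% (0.9).

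**Confidence interval.** In 100,000 simulated arms of 40 with no change, CV 0.70 and rho 0.5, the usual 95% CI of the mean percent change averages −4% to +49%. It lies wholly above zero in about 31% of arms. At CV 0.50 and rho 0.5 it lies wholly above zero in about 20%. At CV 0.70 and rho 0.8 the figure is about 17%.

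**Same case with a log-scale measure.** The SD of ln(Y/X) is √(2 × 0.3988 × 0.5) = 0.632 and its SE is 0.632/√40 = 0.100. The estimate is centred at about 0% and the expected CI is about −18% to +22%. The median percent change is also about 0%.

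**Where exposure does fall.** The same factor understates the fall slightly. For MHBMA with a ratio to baseline of 0.15 (the Table 16 between-arm ratio, used here as an illustration) and rho 0.5, 0.15 × 1.221 = 0.183, so −85% is shown as −81.7%.

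**The case against.** The case on the other side is substantial and narrows the point in several ways.

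- **Figures.** A reader might infer that the mCC graphs will show exposure rising. The documents do not establish that. Figures 15.1.1.2 to 15.1.1.4 are titled as geometric means, no arithmetic percent-change figure is listed for these analyses, and the output shells are in a separate document. What stands is a contradiction between 12.1.3 and the figure titles, and the tables, which are governed by SAP 7 and 12.1.3 in any case.
- **Size.** A reader might take 22% as a ceiling or an expected value. It is neither. It needs rho 0.5, which the documents do not give, and the larger of the plan's two CV sets.
- **Interval.** A reader might infer that the CI would demonstrate a rise. On average it still includes zero at n = 40, even at CV 0.70 and rho 0.5. Nor is this a coverage failure: the interval targets the arithmetic mean percent change, which really is above zero under this model. The trouble is that zero on that scale does not mean no change.
- **Median.** It is already planned for all continuous data and is unaffected, so a careful reader of the tables has a sound figure beside the biased one.
- **Objectives and inference.** Secondary objective 3 in SAP 5.2 is worded in terms of levels, and levels receive geometric means. No test, success criterion or sample size uses percent change. If spread and rho are alike in both arms, the factor cancels from the between-arm ratio.

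These limits are accepted. None of them makes the mean percent change and its CI a good summary for data the SAP itself treats as log-normal.

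**Conclusion.** The point holds, within descriptive outputs. SAP 7 and 12.1.3 specify a measure of change that is biased upward for log-normal biomarkers when there is no true change. Under the assumption rho = 0.5, the bias is about 5% to 22% with the CVs of Tables 16 and 17 and about 1% to 12% with those of Table 18. At CV 0.70 it is 4% to 49% over rho from 0.9 to 0. These figures also assume equal log variance at both times and a median ratio of 1. They concern the tables, and a graph only if one of percent change is actually drawn; COHb percent change is tabulated only. Exhaled CO is outside the point because it is not analysed on the log scale.

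A reader might go further and doubt the primary comparison. That would be wrong: it is a log-scale ANCOVA reported as back-transformed geometric mean ratios, and percent change plays no part in it. This is an inexpensive improvement, not a threat to the trial's conclusions.

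**What to change.** In SAP 7 and 12.1.3, for biomarkers of exposure analysed on the log scale, define the summary change from baseline as the geometric mean percent change, 100·(exp(mean[ln(value) − ln(baseline)]) − 1), with its 95% CI computed on the log scale and back-transformed. Use it in the summary tables and in any percent-change graph, and keep the median. Individual percent changes can stay in the listings.

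Reconcile the graph wording under Urinary BoExp Summaries with the titles of figures 15.1.1.2 to 15.1.1.4, stating for each figure whether it shows levels or change and which mean is plotted.

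The cost is SAP wording and a programming change to outputs already planned. No new data are needed and no test or sample size changes.

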#### Safety Summaries

In general, summaries for the Safety population will be produced by randomization arm, separately for the following periods:

- Pre-Randomization, including safety data collected until randomization. Only for this period, the Safety population includes any subjects who tested the product but were not randomized and these subjects will be reported in a separate “Product Test Only” group.
- Randomized period, including Baseline and all post-Baseline data.

The following product labels will be used throughout the TFLs (**Table 24**):

**Table 24: Product Labels**

Product	Format used in TFLs	Order in TFLs
Tobacco Heating System 2.2 Menthol	THSm2.2	1
Menthol conventional cigarettes	mCC	2
Smoking abstinence	SA	3

The following stratification labels (**Table 25**) for the TFLs will be used:

**Table 25: Stratification Labels**

Stratification Factor	Definition
Product preference (which product the subject would prefer to be randomized to).	THSm2.2 (THS 2.2 Menthol) mCC SA NP (No preference)
Sex	Male Female
Daily mCC consumption (per day)	10-19 >19
Safety Time Periods	Pre-Randomization period ([Product trial – Randomization]) Randomized period Confinement ([Day 1-Day 6 confinement] ) Ambulatory ([Day 6 ambulatory-Day 90 Visit]) Safety Follow-up ([Day 90 Visit – End of Study])
Product Use Time Periods	Period 1 ( [Day 1-Day 6 confinement] ) Period 2 ( [Day 6 ambulatory-Day 30 Visit] ) Period 3 ( ]Day 30 Visit-Day 60 Visit] ) Period 4 ( ]Day 60 Visit-Day 90 Visit] )
Product Use Categories for mCC arm	CC Only (Exclusively CC) CC Dual (Use of other products)
Product Use Categories for SA arm	Abstinent Predominantly Abstinent Not Abstinent
General Product Use Categories for THS 2.2 Menthol arm	THS 2.2 [70-100%] Dual ]30-70%[ CC [0-30%]

PP SetDetailed Product use Categories for THS 2.2 Menthol	Primarily THS 2.2 ([95-100]%) Predominantly THS 2.2 ([70-95]%) Dual Mostly THS 2.2 ([60-70]%) Dual Balanced ([40-60]%) Dual Mostly CC ([30-40]%) Predominantly CC ([5-30]%) Primarily CC ([0-5]%)
---	---

#### 12.1.4 Definitions for Statistical Data Analysis

The following definitions (Table 26) for statistical analyses/presentations will be used:

